11.2 Treatment Administration

11.2.1 Bosutinib Treatment

Patients will take the prescribed 4 tablets of 100 mg or 1 tablet of 400 mg of bosutinib with water and food, at approximately the same time each day (preferably in the morning).

Patients who forget to take their dose more than 12 hours after it is due, should not make up the missed dose. Any missing doses should be recorded, and subsequent training of patients should be documented in the appropriate source record (e.g. clinic chart).

The day that atezolizumab is administered; the patients will take the corresponding dose of bosutinib after the administration of atezolizumab.

A diary card or equivalent where the date and time of administration will be recorded will be provided to the patients.

11.2.2 Atezolizumab Treatment

For the administration of atezolizumab the patient will go to the hospital, in scheduled visit, and will receive 840 mg or 1680 mg, the two therapeutic options available in this study. If the dose is 840 mg, the patient will receive atezolizumab 840 mg every 2 weeks in each cycle, at the beginning of the first day of the cycle, while if the dose is 1680 mg the patient will receive atezolizumab 1680 mg on the first day of cycle (every 4 weeks). The initial dose of atezolizumab must be administered over 60 minutes; if the first infusion is well tolerated, all subsequent infusions may be administered over 30 minutes.

11.3 Formulation, Packaging, and Labeling

11.3.1 Bosutinib Treatment

Bosutinib investigational drug product is supplied as tablets. Each tablet contains either 100 mg or 400 mg of bosutinib as active ingredient. Other ingredients are typical pharmaceutical excipients: in tablet core [Microcrystalline cellulose (E460), Croscarmellose sodium (E468), Poloxamer 188, Povidone (E1201), Magnesium stearate (E470b)] and in film coating [Polyvinyl alcohol; Titanium dioxide (E171); Macrogol 3350; Talc (E553b); Iron oxide yellow (E172), Iron oxide red (E172) (only in the 400 mg tablets)]. Tablets will be supplied as follows:

- White opaque 3-ply PVC/Polychlorotrifluoroethene/PVC blister sealed with push-through foil backing containing either 14 or 15 tablets per blister (2 blisters in each package).**

Carton labels will bear the appropriate label text as required by governing regulatory agencies. Such text will include, at least, product name, product strength, number of tablets, lot number and expiration date.

Bosutinib will not be dosed by weight or body surface area.

11.3.2 Atezolizumab Treatment

Atezolizumab investigational drug product is supplied as a concentrate solution for infusion. Each vial of concentrate contains 840 mg of atezolizumab (Atezolizumab is an Fc-engineered, humanized IgG₁ anti-programmed death-ligand 1 [PD-L1] monoclonal antibody produced in Chinese hamster ovary cells by recombinant DNA technology). Other ingredients are typical pharmaceutical excipients: L-histidine, Glacial acetic acid, Sucrose, Polysorbate 20, and Water for injections. Vials will be supplied as follows:

- Vial of 840 mg: Type I glass vial with a butyl rubber stopper and an aluminum seal with a plastic, grey flip-off cap containing 14 mL of concentrate for solution for infusion.**

Carton and vial labels will bear the appropriate label text as required by governing regulatory agencies. At a minimum, such text will include product name, product strength, number of tablets, lot number and expiration date.

Atezolizumab will not be dosed by weight or body surface area.

11.4 Treatment Storage, Dispensing, and Accountability

All investigational treatment is to be stored in a secure locked area while under the responsibility of the principal investigator. An authorized person at the investigator's site must record receipt and dispensing of investigational treatments.

The study pharmacist or designee at the investigative site will be responsible for handling and dispensing study drug and completing associated documentary paperwork.

The Investigator will confirm receipt of the investigational product in writing (date and storage conditions).

Supplies will be shipped to the investigative site at appropriate intervals, depending on patient accrual. The site must use either an appropriate dispensing log/accountability form provided by the sponsor or an acceptable substitute. Each time study medication(s) is dispensed for a patient, the following information is recommended to be recorded: the patient's study number, tablet and vial strength, the number of tablets (with the corresponding lot number) and vials dispensed, and the initials of the person dispensing the drug. These logs are to be maintained by the study investigator and will be periodically verified by a representative of the sponsor. The principal investigator is responsible for ensuring that the patient diary card(s) and study drug provided to the patient and returned from the patient are accounted for and noted in source documentation.

The responsible CRA will check the drug supply for inventory purposes and to ensure proper storage at regular intervals throughout the study.

11.4.1 Bosutinib Treatment

The recommended storage condition for bosutinib is $\leq 30^{\circ}\text{C}$.

Patients will receive bosutinib at 400 mg/day orally. Bosutinib will be self-administered by the patient on a daily schedule.

The investigator will dispense the bosutinib to the patients every 3 cycles, starting at the time when the patient is included in the clinical trial. Patients will have sufficient medication to continue treatment until the next dispensed medication-visit is scheduled, even if it takes place out of visit the window of plus 14 days. Unused medication and empty blister cards should be returned to the site at dispensed medication-visits and will not be dispensed again.

11.4.2 Atezolizumab Treatment

Atezolizumab must be stored in a refrigerator ($2^{\circ}\text{C} - 8^{\circ}\text{C}$).

Patients will receive an intravenous dose of 840 mg of atezolizumab every 2 weeks or 1680 mg every 4 weeks administrated by the investigator in the site.

The first infusion of Atezolizumab should be given intravenously over 60 minutes. If this infusion is tolerated, all subsequent infusions may be delivered over 30 minutes.

11.5 Treatment Duration

The patients included will remain in the study for at least 100 weeks, 4 weeks (1 cycle) in the first treatment phase, 48 weeks (12 cycles) in the second treatment phase, and 48 weeks (12 cycles) in the third treatment phase), unless discontinue early.

The First 10 Patients:

- First cycle, they will receive bosutinib 400 mg/day in monotherapy.
- Second and third cycles, they will receive bosutinib 400 mg/day in combination with atezolizumab 840 mg every two weeks.
- If no safety issues are detected, these patients will cross-over from bosutinib 400 mg/day plus atezolizumab 840 mg every 2 weeks to bosutinib 400 mg/day plus atezolizumab 1680 mg every 4 weeks for 10 more cycles.
- After 12 cycles of treatment with bosutinib plus atezolizumab combination, the patients will continue with bosutinib 400 mg/day in monotherapy for 12 more cycles.

Other 26 Patients:

- First cycle, they will receive bosutinib 400 mg/day in monotherapy.
- Second cycle, they will receive bosutinib 400 mg/day plus atezolizumab 1680 mg every 4 weeks for 12 cycles.
- After 12 cycles of treatment with bosutinib plus atezolizumab combination, the patients will continue with bosutinib 400 mg/day in monotherapy for 12 more cycles.

If, at any point during the treatment with bosutinib 400 mg/day plus atezolizumab 1680 mg every 4 weeks, 2 or more patients experience DLTs, atezolizumab dosage will change to 840 mg every 2 weeks.

11.6 Dose Modification and Dose Delay

The following section summarizes dosing modifications of bosutinib or atezolizumab to manage possible toxicity. Administration of bosutinib or atezolizumab could be stopped for an individual subject in the event of a treatment-related toxicity that, in the Investigator's assessment, warrants discontinuation. Exceptions to these guidelines will require approval from the Medical Monitor.

A maximum discontinuation of 1 month is allowed for the treatment with bosutinib if required due to the onset of adverse events, investigator decision, or other major circumstances. If a subject discontinued treatment for more than one month he/she will be withdrawn from the study and the appropriate follow-up procedures will be conducted. Also, to be included in the

efficacy analysis (Per protocol set population), a subject must comply with at least 70% of treatment with bosutinib. Regarding atezolizumab treatment, fail to administrate up to 3 out of the 11 administrations scheduled, will be allowed to continue in the study. If, for any reason, atezolizumab could not be administered 4 or more times during the course of the study, the subject will be withdrawn from the study and the appropriate follow-up procedures will be conducted. All deviations from the scheduled treatments regime shall be recorded in the patients' clinical history and the eCRF and explained if required.

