9.3 Second Therapy

9.3.1 Group 1: The first 10 patients

Only for the first ten patients included in the study, atezolizumab will be introduced at a dose of 840 mg every two weeks combined with 400 mg/day of bosutinib for 2 cycles (8 weeks). These patients will be closely monitored for safety issues.

If dose-limiting toxicities (DLTs) appear in 2 or more patients the study will end.

A DLT would include either of the following adverse events that occurred during bosutinib therapy in combination with atezolizumab, if it is considered at least possibly related to bosutinib and/or atezolizumab:

- Grade 4 neutropenia (<500/ μ l) persisting for > 7 day duration or Grade 4 white cell count decrease for >7 day duration (<1000/ μ l).
- Febrile neutropenia (ANC<1000/ μ l and fever \geq 38.5°C).

- Grade 4 thrombocytopenia > 48 hour duration or with bleeding requiring platelet transfusion.
- Any Grade 3 or 4 clinically evident non-hematological toxicity.
- Any ≥Grade 3 toxicity that requires >14 days to resolve (to ≤Grade 1 despite optimal medical therapy).

DLTs will be graded according to the NCI CTCAE, v5.0.

If no relevant safety issue, regarding the combination is detected the study will continue.

These initial 10 patients will cross-over from bosutinib 400 mg/day plus atezolizumab 840 mg every 2 weeks to bosutinib 400 mg/day plus atezolizumab 1680 mg every 4 weeks for 10 cycles (40 weeks).

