11.6.2.1 Pulmonary Events

Dyspnea, cough, fatigue, hypoxia, pneumonitis, and pulmonary infiltrates have been associated with the administration of atezolizumab.

All pulmonary events should be thoroughly evaluated, as follows, for other commonly reported etiologies such as pneumonia/infection, lymphangitic carcinomatosis, pulmonary embolism, heart failure, chronic obstructive pulmonary disease, or pulmonary hypertension. For specific management guidelines, please see table 3.

Table 3. Management Guidelines for Pulmonary Events, including pneumonitis

Adverse Event	Management
Pulmonary event, Grade 1	
Continue atezolizumab and monitor closely.Re-evaluate on serial imaging.Consider subject referral to pulmonary specialist.
Pulmonary event, Grade 2	
Withhold atezolizumab for up to 12 weeks after event onset.^aRefer subject to pulmonary and infectious disease specialists and consider bronchoscopy or BAL.Initiate treatment with 1-2 mg/kg/day oral prednisone or equivalent.If event resolves to Grade 1 or better, resume atezolizumab.^bIf event does not resolve to Grade 1 or better while withholding atezolizumab, permanently discontinue atezolizumab and contact Sponsor.^c
Pulmonary event, Grade 3 or Grade 4	
Permanently discontinue atezolizumab and contact the Sponsor.^cBronchoscopy or BAL is recommended.Initiate treatment with 1-2 mg/kg/day oral prednisone or equivalent.If event does not improve within 48 hours after initiating corticosteroids, consider adding an immunosuppressive agent.If event resolves to Grade 1 or better, taper corticosteroids over ≥ 1 month.

BAL=bronchoscopic alveolar lavage; IVIG=intravenous immunoglobulin

a. Atezolizumab may be withheld for a longer period of time (ie, >12 weeks after event onset) to allow for corticosteroids (if initiated) to be reduced to ≤ 10 mg/day oral prednisone or equivalent. The acceptable length of the extended period of time must be agreed upon by the investigator and the Sponsor.

b. If corticosteroids have been initiated, they must be tapered over ≥ 1 month to ≤ 10 mg/day oral prednisone or equivalent before atezolizumab can be resumed.

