12 VISIT SCHEDULE AND ASSESSMENTS

12.1 Schedule of Events

Details on scheduling and sample collection are described in Tables 14-17. The tables 14 and 15 for 1st group of patients (first 10 patients included), and the tables 16 and 17 for 2nd group of patients (the last 26 patients included).

All data obtained from these assessments must be recorded in the source documentation. The CRF will not be used as a source document for any study data.

Please maintain a special awareness of the assessments of the primary and secondary endpoints.

All visits should be completed on the designated day or as close as possible. However, the windows allowed by protocol will be:

- For visits that take place every two weeks, the window will be ± 3 days.
- For visits that take place every 4 weeks, the window will be ± 3 days.
- For visits that take place every 3 cycles (every 12 weeks), and the End of Treatment visit, the window allowed will be ± 14 days.

For this purpose, a cycle equal to 28 days (4 weeks) will be defined and one month will be considered to be equivalent to one cycle.

Table 14. Schedule of Assessments 1st and 2nd Therapies for the First 10 Patients

The following visit schedule will apply if the atezolizumab dose does not need to be adjusted during 2nd therapy due to DLTs. If the dose of atezolizumab has to be modified to the 840 mg every two weeks, additional visits will be scheduled for the administration of atezolizumab. The only procedure to be conducted during these additional visits is the administration of atezolizumab

1 st Group of Patients (The 10 First Patients)		1 st Therapy		2 nd Therapy													
VISIT	Visit 0	Visit 1	Visit 2	Visit 3	Visit 4	Visit 5	Visit 6	Visit 7	Visit 8	Visit 9	Visit 10	Visit 11	Visit 12	Visit 13	Visit 14	Visit 15	Visit 16
Cycle	Screening / Baseline	Cycle 1		Cycle 2		Cycle 3		Cycle 4	Cycle 5	Cycle 6	Cycle 7	Cycle 8	Cycle 9	Cycle 10	Cycle 11	Cycle 12	Cycle 13
Day within Cycle (Visit Window ± 3 Days)	-28/-1	1	15	1	15	1	15	1	1	1	1	1	1	1	1	1	1
Consecutive Days in the Study (D)	-28/-1	D1	D15	D29	D43	D57	D71	D85	D113	D141	D169	D197	D225	D253	D281	D309	D337
Informed Consent	X																
Eligibility	X	X ⁽¹⁾															
Inclusion/Exclusion Criteria (Checklist)	X	X ⁽¹⁾															
Medical/Surgical History and Demographics	X																
Recent Medication Prior to First Dose of IMP	X	X ⁽¹⁾															
Leukemia Diagnosis and Prior Cancer Therapy	X																
Sokal Risk Score	X																

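### The withdrawal limit of 4 missed atezolizumab infusions ignores the dose interval: a permitted 12-week toxicity hold fits it on 1680 mg every 4 weeks but exceeds it on 840 mg every 2 weeks and in Group 1's run-in

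*Protocol*

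**What the plan says.** **The withdrawal rule.** Protocol 11.6 states that if "atezolizumab could not be administered 4 or more times during the course of the study, the subject will be withdrawn from the study". Protocol 9.5, Protocol 12.19 and SAP 5.3 repeat the limit. None of the four places mentions the dose or the interval. Sections 11.6 and 12.19 also describe the allowance as up to 3 misses out of a scheduled total of 11.

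**The toxicity tables.** Table 3 (Protocol 11.6.2.1) says for a Grade 2 pulmonary event: "Withhold atezolizumab for up to 12 weeks after event onset". It then directs resumption on recovery to Grade 1 or better. Tables 4 to 11 contain the same 12-week allowance for at least one event and grade. The footnotes add a condition on resuming, "If corticosteroids have been initiated, they must be tapered over ≥ 1 month to ≤ 10 mg/day oral prednisone or equivalent", and a possible extension agreed between investigator and Sponsor: "Atezolizumab may be withheld for a longer period of time (ie, >12 weeks after event onset) to allow for corticosteroids". The tables do not distinguish 2-weekly from 4-weekly dosing.

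**The schedules.** Group 1 receives 840 mg every 2 weeks in cycles 2 and 3, then 1680 mg every 4 weeks for 10 cycles. Group 2 receives 1680 mg every 4 weeks for 12 cycles. Protocol 11.5 adds a fallback during treatment at 1680 mg: if "2 or more patients experience DLTs, atezolizumab dosage will change to 840 mg every 2 weeks".

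**Relief.** Section 11.6 also says: "Exceptions to these guidelines will require approval from the Medical Monitor".

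**The concern.** The same 12 weeks without atezolizumab means a different number of missed infusions on each schedule. A limit set as a fixed count is therefore stricter for patients dosed every 2 weeks, although the planned total dose is the same. A patient managed exactly as the toxicity tables direct could be withdrawn while those tables still allow resumption.

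Withdrawal stops study bosutinib and the scheduled BCR-ABL assessments. The Full Analysis Set requires completion of the 12 combination cycles (Protocol section 4), so a patient withdrawn during combination also leaves that set and hence the Per-Protocol Set. Only 30-31 patients are expected to receive the combination (Protocol 15.5), so each avoidable loss weighs on the molecular-response results.

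**Working it through.** **Inputs.** The cycle is 28 days, and Protocol 12.1 adds that "one month will be considered to be equivalent to one cycle". The infusion days come from Tables 14 and 16; the limit is 4 misses; the hold is 84 days from onset.

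**Step 1: the stated total of 11.**
- Group 1: days 29, 43, 57, 71 (840 mg), then day 85 and every 28 days to day 337 (1680 mg): 4 + 10 = 14 infusions.
- Group 2: day 29 and every 28 days to day 337: 12 infusions.
- 840 mg every 2 weeks throughout: 2 × 12 = 24 infusions.

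None equals 11. All three give the same total dose: 4 × 840 + 10 × 1680 = 12 × 1680 = 24 × 840 = 20,160 mg.

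**Step 2: infusions missed in a full hold.** Count the scheduled days s with onset ≤ s < onset + 84. Holds that run past the last infusion miss fewer.

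| Schedule and onset | Missed days | Number | Fourth miss, days after onset |
|---|---|---|---|
| 4-weekly, any onset | – | 3 | 84-111 |
| 2-weekly, any onset | – | 6 | 42-55 |
| Group 1, D30-43 | 43, 57, 71, 85, 113 | 5 | 42-55 (D85) |
| Group 1, D44-57 | 57, 71, 85, 113 | 4 | 56-69 (D113) |
| Group 1, D58-71 | 71, 85, 113, 141 | 4 | 70-83 (D141) |
| Group 1, D72 or later | 4-weekly infusions only | 3 | 84 or more |

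**Step 3: share of planned dose missed at the fourth miss.**
- 4-weekly: 4 × 1680 / 20,160 = 33%.
- Continuous 2-weekly: 4 × 840 / 20,160 = 17%.
- Group 1 windows in turn: (3 × 840 + 1680) / 20,160 = 21%; (2 × 840 + 2 × 1680) / 20,160 = 25%; (840 + 3 × 1680) / 20,160 = 29%.

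**Step 4: can a real hold last that long?** If corticosteroids were started, the taper takes at least 28 days. The hold then reaches the fourth miss if the taper starts later than (fourth-miss day − 28):
- 2-weekly, or Group 1 D30-43: 14-27 days after onset.
- Group 1 D44-57: 28-41 days.
- Group 1 D58-71: 42-55 days.
- 4-weekly: 56-83 days, and only through a hold extended beyond 12 weeks.

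**Step 5: exposure without the switch.** At most 10 patients (Group 1), with onset on 71 − 30 + 1 = 42 of the 336 combination days (D29-364): 42 / 336 = 12.5%.

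**Step 6: the same holds in 1680 mg equivalents** (840 mg = 0.5; every course totals 12).
- 4-weekly: 3 × 1 = 3.0. Continuous 2-weekly: 6 × 0.5 = 3.0.
- Group 1: D30-43, 3 × 0.5 + 2 = 3.5; D44-57, 2 × 0.5 + 2 = 3.0; D58-71, 0.5 + 3 = 3.5; D72 or later, 3.0.
- Over every possible cycle for a switch from 4-weekly to 2-weekly dosing, in both groups, the maximum is 3.5.

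These figures assume that an infusion due on day 84 is given. If it too is missed, onset on a 4-weekly infusion day, or on D57 in Group 1, reaches 4.0.

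**The case against.** **The rules do not contradict each other.** Twelve weeks is a ceiling on resuming the drug, and the 4-miss limit governs staying in the study. Both can be followed, with the stricter one deciding, and no section promises that every permitted hold preserves participation. This stands, but it does not explain why the limit should bite at half the missed dose on one schedule.

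**Infusions might be postponed.** The count assumes they are missed. The protocol does not say so outright, but it has no make-up rule for atezolizumab and its infusion calendar is fixed. This remains an assumption.

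**Few patients are exposed.** This largely stands. The Group 1 window lies inside the 2-cycle DLT period, and two patients with DLTs end the study. What remains is mainly Grade 2 events that resolve slowly. The taper condition applies only if corticosteroids were started; Grade 2 ocular events, for example, get topical treatment. The fallback to 2-weekly dosing needs 2 or more patients with DLTs at 1680 mg. As an illustration only, with 30 patients and an assumed independent DLT risk p for each, the chance is 1 − (1 − p)^30 − 30p(1 − p)^29: 45%, 82% and 99% for p = 5%, 10% and 20%. The documents give no value for p.

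**Exceptions exist.** The Medical Monitor clause is a real remedy for single patients. It does not correct the rule, and Protocol 9.5 and SAP 5.3 repeat the limit without it.

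**Stronger readings that the documents do not support.** A reader might infer that any long hold forces withdrawal; only holds lasting past the fourth miss do. A reader might infer that 4-weekly dosing is affected too; a 12-week hold fits there, and only an extended hold or a further miss reaches four. A reader might infer that all follow-up ends; the definition of premature withdrawal keeps monitoring for progression and survival, and there is an early-termination visit and 28-day safety follow-up.

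**Conclusion.** The concern holds in limited form. The limit takes no account of dose or interval, so a 12-week hold that fits it on 1680 mg every 4 weeks exceeds it on 840 mg every 2 weeks and, for onset on days 30-71, in Group 1. A patient can then be withdrawn while resumption is still permitted. The total of 11 scheduled administrations is wrong in its own right, but the conclusion does not depend on it.

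This rests on nominal visit days, on withheld infusions being missed, and on the infusion due on day 84 being given. The number of patients affected cannot be estimated from the documents. It would be wrong to infer damage to the primary analysis: the Safety Set needs only one dose of study medication, so withdrawn patients stay in it. The cost falls on retention and on the sets that require completion of the combination. The rule should be corrected, but it does not threaten the trial's main conclusion.

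**What to change.** In Protocol 9.5, 11.6 and 12.19 and SAP 5.3, replace the count with wording such as:

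*Missed atezolizumab is counted in 1680 mg equivalents: a missed 1680 mg infusion counts 1 and a missed 840 mg infusion counts 0.5. A subject who misses 4 or more of the 12 scheduled equivalents is withdrawn.*

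In Protocol 11.6 and 12.19, replace the allowance of 3 out of 11 with: *fewer than 4 of the 12 scheduled equivalents*. State also that an infusion due on day 84 of a hold is to be given if the criteria for resuming are met.

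Holds extended beyond 12 weeks should stay with the existing Medical Monitor exception. An automatic, uncapped exemption would go too far: on 4-weekly dosing, a hold from day 57 to the end of combination would miss 11 of 12 infusions but count only 3.

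The cost is a wording amendment in four places. No new data are needed, because 11.6 already requires deviations from the treatment schedule to be recorded. The limit on a purely 4-weekly course does not change. The small downside is that a full 2-weekly course would tolerate up to 7 missed infusions (7 × 840 / 20,160 = 29% of planned dose), including misses unrelated to safety. Permanent discontinuation of atezolizumab with 4 or more equivalents left would still lead to withdrawal, as now.
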